For only women in this 'revised' biological R01 study: All 300 women (intervention, EUC, and healthy control) in the supplement grant application will receive baby gifts (up to \$10) at the completion of the study as a thank you.

During our preliminary formative research (IRB #7678) during the last year, we conducted in-depth interviews with expectant mothers experiencing anxiety (n=19) and health professionals (n=10) to identify risk factors, means of expressing anxiety, current coping strategies, and the acceptability and feasibility of a facility-based intervention targeting anxiety among expectant women. The content and strategies employed by HMHB are informed by the findings of our

formative study and other relevant literature. Evidence-based strategies for managing anxiety and behavior activation are used in HMHB. Psychosocial risk factors of anxiety such as adverse life events, interpersonal problems, lack of social support, pregnancy complications, and fear of labor are addressed in the intervention.

The dosage of the HMHB is informed by evidence from the literature. The United Kingdom National Institute for Health and Care Excellence (NICE) guidelines recommends between five and seven individual CBT-based sessions for anxiety management. Recent systematic reviews of CBT-based perinatal anxiety interventions indicate that 6 to 12 sessions were effective in reducing symptoms of perinatal anxiety.(99, 100) The HMHB intervention consists of six core sessions and between two and six booster sessions. Core sessions focus on (1) psycho-education and stress management, (2) personal wellbeing, (3) social support, (4) mother-infant bonding during pregnancy, (5) relapse prevention, and (6) preparation for the baby and early postnatal period. The first five core sessions will be delivered weekly to ensure that expectant women receive maximum dosage as early in their pregnancy as possible. The sixth session will be delivered later, in the third trimester. Booster sessions will be delivered during the expectant women's routine antenatal visits to the hospital between the fifth and sixth core sessions. Based on at what gestational week a woman is recruited into the study, each woman will receive between two and six booster sessions. Sessions will last between 45 minutes and an hour. Family member/s will be invited to attend the first, third, and sixth core sessions

Table 1 indicates the active ingredient and timing of each session for the intervention arm.

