All assessments will be in the hospital, and we will attempt to pair them with her regular prenatal and postnatal medical visits when possible.

3. Describe the expected duration of the study from the perspective of the individual participant and duration overall.

Sessions will last between 45 minutes and an hour, and data collection will extend from the time of enrolment in early pregnancy ( $\leq 22$  weeks gestation) until the 6 week postpartum-end-point assessment.

Those who are randomized to the intervention arm will additionally experience the intervention. Please see Tables 1 and 2 for an outline of sessions for intervention and control participants, respectively.

4. Provide a brief data analysis plan and a description of variables to be derived.

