#### Analysis of Variables from Biological Substudy

**Statistical Analysis.** Oversight for the statistical analyses will be provided by [name] of the Johns Hopkins Biostatistics Center. The initial statistical approach will include a descriptive cross-sectional analysis at each time point, both for quality assurance and to attain a better understanding of the distributions of the outcome variables for use in subsequent analyses, including the need for any transformations, followed by the longitudinal analyses. For **Aim 1**, we will assess the associations between cytokine levels as dependent variables and level of anxiety (as measured by the HADS) as the independent variable. The level of anxiety will be considered from the following perspectives: 1) dichotomous (above and below HADS=8) and 2) continuous. In both analyses, we will compare women with anxiety vs. healthy controls and with and without the intervention to evaluate whether there is a positive association between

cytokines and other immune markers with anxiety. In addition, we will perform a comparison of immune markers between women disease/intervention groups adjusted for potential confounders that are differentially distributed by disease group, using multivariable linear regression model at each time point. We will assess whether association between immune marker and anxiety is different by group and by visit. In the longitudinal analyses, we will fit generalized linear mixed effect models to account for within-woman correlation of inflammatory markers. The model will include indicators for visit and group as well as any relevant interaction terms (e.g. group by visit). The models will adjust for baseline severity and other patient characteristics. A random effect for woman will be included as a random intercept. Other, more complex model structures will be explored, such as a model with random slope or non-independent residual correlation structure. These models account for missing at random, i.e. missing data are assumed to depend on prior immune marker values and covariates. Standard model checking will be performed and the most parsimonious model will be selected based on the Akaike Information Criterion (AIC).

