**Biological Outcome Variables:** Subjects will have their blood drawn (up to 20 ml) at all four visits by a study clinician or a research assistant trained in phlebotomy. Each participant will be scheduled as close to possible to the same time of day during the morning hours for all four blood draws (as blood is drawn in HFH between 8:00am and 1:00 pm), allowing us to control for diurnal variation in cytokine levels. Blood will be collected in sodium-heparin tubes for immune cell preparation. Blood will be centrifuged within 8 hours of collection by low-density gradient centrifugation via a Z326 High Performance Centrifuge. Plasma will immediately be frozen in cryovials at -80 C in a ThermoScientific Revco RLE Ultra-Low Lab Freezer and will be stored there until it is shipped to Baltimore for analysis at the end of the trial.

**Shipping of Samples:** Plasma samples (approximately 4800 cryovials) will be shipped from Pakistan to Baltimore at the end of the trial for analysis using Federal Express courier services. Blood will stay frozen at a minimum of -20 throughout shipment, using standard cold packs, dry ice, or liquid nitrogen as required by local regulations and the standards of the courier services. Because we will not be able to maintain a temperature of -80 during shipping, we plan to use multiple shipments (6-8) so that we can initiate analysis immediately upon arrival in Baltimore to avoid freeze-thaw cycles. (Shipping all vials at once will yield a batch too large for the capacity of our laboratory and staff to process at once.) Leftover samples will be refrozen for possible additional future analyses and will be stored in [name] lab at the Women's Mood Disorders Center, Johns Hopkins School of Medicine.

**Blood Sample timing:** Targets times for sampling blood will be at baseline (between 10 and 22 weeks), during the second trimester (24 weeks  $\pm$  2), the third trimester (36 weeks  $\pm$  2) and at 6 weeks  $\pm$  2 postpartum). All samples will be drawn in the morning (between 8:00 am and 1:00 pm) to minimize differences due to diurnal fluctuations in cytokine levels.

- If genetic/genomic analyses are planned, address whether the data will be contributed to a GWAS or other large dataset. Address returning unanticipated incidental genetic findings to study participants.

N/A

- If clinical or laboratory work will be performed at JHU/JHH, provide the JH Biosafety Registration Number.

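### Biological substudy: the draw-time rules leave up to five hours of between-woman difference, and neither draw time nor the wait before centrifugation is recorded or modelled.

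*Combined protocol and SAP*

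**What the plan says.** Collection is described in section V, under Biological Outcome Variables and Blood Sample timing; the draw-time and processing text also appears under Baseline. Two rules limit diurnal variation.

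- Within a woman: "Each participant will be scheduled as close to possible to the same time of day during the morning hours for all four blood draws".
- Across all women: "All samples will be drawn in the morning (between 8:00 am and 1:00 pm) to minimize differences due to diurnal fluctuations in cytokine levels".

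On processing: "Blood will be centrifuged within 8 hours of collection by low-density gradient centrifugation". Immediate freezing is promised only for the plasma obtained afterwards.

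The analysis is in Analysis of Variables from Biological Substudy. For each visit, "we will perform a comparison of immune markers between women disease/intervention groups adjusted for potential confounders that are differentially distributed by disease group". The longitudinal mixed models contain visit, group, their interaction and a random intercept for woman, and "The models will adjust for baseline severity and other patient characteristics". Aims 2 and 3 follow the same approach.

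The healthy controls are recruited separately and are not randomized (section V, item on assigning participants). Of the assessments, the plan says "we will attempt to pair them with her regular prenatal and postnatal medical visits when possible". HMHB booster sessions take place at "routine antenatal visits to the hospital between the fifth and sixth core sessions".

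**The concern.** A stable draw time removes the clock effect from a woman's own change between visits. It does not remove it from a comparison between women. There, a woman who is always bled at 8:30 and one who is always bled at 12:30 differ by a constant amount that four draws do not average away. The random intercept treats that amount as woman-level variance; it does not correct a difference in mean draw time between groups.

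The plan itself treats time of day as a source of cytokine variation worth controlling. If healthy controls attend at different hours from anxious women, part of an apparent immune phenotype of anxiety could be a clock or processing effect. The same applies to between-woman associations of markers with symptoms. If the times are never written down, the question cannot be settled later.

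**Working it through.** **Planned precision.** The substudy sample size section gives 60 women per group, four measures, correlation 0.6, alpha 0.05 and effect sizes of 0.3 to 0.5. Enrolment reproduces: 300 × (1 − 0.40) = 180, or 60 per group. For a four-draw mean the variance factor is (1 + 3 × 0.6)/4 = 0.70. With a two-sided test (sidedness is not stated), power is 90.5% at 0.5. At 0.3 it is 50.2%, short of the stated 80%; that is a separate matter and not part of this point.

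**Assumptions.** The documents give neither the slope b (SD per hour of draw time) nor the gap D in mean draw time between groups. I take b = 0.05, 0.10 and 0.20, that is 0.25, 0.5 and 1.0 SD over the five-hour window, and D = 1 hour.

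**Bias.** Bias = b × D.

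**Single visit, 60 v 60.** SE = √(2/60) = 0.183 SD.

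**Four-draw mean, 60 v 60.** If each woman's time is fixed and times are uniform over the window, the clock adds b² × 25/12 to the between-woman variance, so SE = √[(0.70 + b² × 25/12) × 2/60].

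| b (SD/h) | Bias at D = 1 h | Share of 0.3 | Type I error, one visit | Type I error, four-draw mean |
|---|---|---|---|---|
| 0.05 | 0.05 SD | 17% | 5.9% | 6.2% |
| 0.10 | 0.10 SD | 33% | 8.5% | 9.9% |
| 0.20 | 0.20 SD | 67% | 19.5% | 23.6% |

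For 60 healthy women against 120 anxious women pooled, the four-draw figures are 6.6%, 11.6% and 29.8%.

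**Simulation (4,000 runs per setting).** Fixed draw times, 60 v 60, four-draw means:

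- D = 1 h, clock time omitted: type I error 5.8%, 10.1% and 24.4%.
- D = 1 h, clock time in the model: bias about 0, error about 5%.
- D = 0, clock time omitted: bias about 0, error about 5%.
- Change between two visits at the same hour: bias about 0, error about 5%.

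**Noise alone.** With D = 0 the added variance b² × 25/12 is 0.005, 0.021 and 0.083. Power at 0.5 moves from 90.5% to 90.3%, 89.7% and 87.2%.

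**HMHB against EUC.** Randomization balances draw times on average at baseline, and the same-time rule then carries that balance forward. Boosters fall only between core sessions 5 and 6, so they cannot touch the baseline or postpartum draws. If every HMHB woman were nevertheless bled an hour later at both the 24-week and third-trimester draws, the shift in the four-draw mean would be (0 + 1 + 1 + 0)/4 = 0.5 h. The bias would be 0.025 to 0.10 SD and, with SE = √(0.70 × 2/60) = 0.153, the error about 5.3% to 10%.

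**Processing delay.** The same reasoning applies to the wait of up to eight hours, but the documents give nothing from which to size it.

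**The case against.** The strongest reply is that the plan already has two controls. The morning window does restrict variation between women, and the text claims only that it minimizes differences. That stands: it would be wrong to infer that scheduling does nothing between women. What remains is the five hours inside the window.

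A reader might also infer that booster sessions push HMHB draws an hour later and so bias the randomized comparison. The documents do not support this. Nothing says a session precedes the draw, two of the four draws cannot coincide with a booster, and the shift arises only if the same-time rule fails.

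The confounder clause for the per-visit models could admit draw time if it were found to differ by group, and the plan defers detail to a statistical analysis plan to be finalized before unblinding. But that clause cannot adjust for a variable nobody recorded. The longitudinal models name patient characteristics, whereas these times belong to the draw. Assaying cases next to matched controls, as the cytokine section describes, deals with assay conditions; the matching factors are not stated.

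Finally, every magnitude here rests on assumed slopes and gaps. That stands too.

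**Conclusion.** The gap is real but modest. Scheduling controls clock time within a woman and reduces it between women; the remainder is neither recorded nor modelled, and the same is true of the processing wait. The exposure lies chiefly in the non-randomized comparison of anxious with healthy women and in between-woman marker associations. HMHB against EUC is exposed only if draw times drift apart by arm at the 24-week or third-trimester draws. Group-by-visit contrasts are protected as long as each woman keeps her hour.

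Under the assumed 0.05 to 0.20 SD per hour and a one-hour gap, the bias is 0.05 to 0.20 SD and the single-visit type I error about 6% to 20%. The upper figure needs a full SD of drift across the morning. With equal mean times there is no bias, and even the steepest assumed slope costs only about 3 points of power (90.5% to 87.2% at an effect of 0.5).

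Two further inferences should be resisted. The documents cite diurnal variation for cytokines only, so they give no basis for extending this to the allopregnanolone outcomes. The trial's primary endpoint is not affected. This is an inexpensive improvement to a secondary study.

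**What to change.** - **Collection (Biological Outcome Variables, Blood Sample timing and the matching Baseline text).** Record clock time of draw and times of centrifugation and freezing for every sample. State that fixed scheduling controls diurnal variation within a woman, and that the window reduces but does not remove it between women.
- **Analysis (Analysis of Variables from Biological Substudy).** Prespecify clock time of draw and hours from draw to centrifugation as draw-level covariates in the immune-marker models for Aims 1 and 3. Report both by group and visit. If a day's samples are all spun at one fixed hour, delay is that hour minus draw time, and one term carries both.
- **Visit order.** If it is standardized, bleed every woman on arrival regardless of arm, so that the order does not reveal allocation to the masked assessors.

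The cost is a few log entries per sample and a few degrees of freedom, with no extra visits or blood. If draws have already begun, earlier samples may lack times; the number without them should be reported by group.

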## JHSPH IRB Research Plan for New Data Collection

*Use this template for new data collection and if you also will analyze secondary data. Answer the questions below and for numbered sections that do not pertain to your study, retain the section numbers and bolded questions, and write "N/A". Please start typing in the gray boxes provided.*

**PI Name:** [name]

**Study Title:** Happy Mother, Healthy Baby (HMHB) – Anxiety-focused early prenatal intervention for prevention of common mental disorders in Pakistan: An individual randomized clinical trial

**IRB No.:** 9177

**PI Version No. / Date:** April 1, 2022

**I. Aims of the Study:** Describe the aims/objectives of the research and/or the project's research questions or hypotheses.

**This IRB application focuses on the randomized clinical trial that will be conducted after the formative phase of our research (formative work approved, IRB#7678).**

In the primary study, we will evaluate the effectiveness of an evidence-informed, anxiety-focused early prenatal prevention intervention on prevalence of Common Mental Disorders (CMDs) in pregnant women at six weeks' postpartum. We hypothesize that randomization of women with subclinical to clinical levels of prenatal anxiety to the intervention arm will result in fewer cases of CMDs (both Generalized Anxiety Disorder (GAD) and Major Depressive Episode (MDE)) at six weeks' postpartum relative to the routine care arm of mothers with similar levels of baseline anxiety who are not receiving the intervention.

**Primary:** The primary objective of the trial is to evaluate the effect of an evidence-informed, anxiety- focused early prenatal prevention intervention in pregnant women, compared with usual care alone, on prevalence of Common Mental Disorders (CMDs) at six weeks' postpartum.

**Secondary:** Secondary objectives include evaluating the impact of the intervention on prevalence of small-for-gestational age (SGA) at birth, preterm birth (PTB) and low birthweight (LBW) as well as the cost-effectiveness of the intervention. We will examine potential mediators of CMDs and whether the effect of the intervention on CMDs and birth outcomes varies by self-reported perceived stress, quality of marital relationship, empowerment, social support, or history of intimate partner violence.

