In our study, the unit of randomization is an individual woman, with an equal number of women randomized to the intervention and control groups. We assume an outcome prevalence of CMDs (postnatal depression episode and anxiety) at 30%, which is conservative given that most estimates of prenatal depression in Pakistan are higher than this. (16, 17, 91, 129) While we observed a 50% reduction in postnatal depressive symptoms when evaluating our prior CBT intervention (which was initiated late in pregnancy), we desire 85% power to detect reductions in CMDs as low as 30% (86, 130, 131), requiring 840 pregnant women (420 in each arm). Anticipating 30% attrition post enrollment, we will enroll 600 women per group in this study, for a total of 1200 women. This sample size of 420 outcomes per group provides ample power to detect important reductions in SGA, which we currently estimate to occur in approximately 47% of births. For example, we will have 90% and 80% power to detect reductions of 23.7% and 20.2%, respectively.

Sample size considerations for the qualitative process evaluation/COVID-questions will be based on a target number of up to 80 women sampled across different characteristics, or until saturation is achieved. We will sample up to 45 women from the intervention group and 25 women from the EUC group and another 10 who dropped out of the intervention. As described (See under Study Design above), these women will be purposively sampled to achieve a wide range of variation (or maximum variation) on various dimensions of interest. To triangulate and learn from multiple perspectives, we will also hold 2 focus group discussions (FGDs) with the HMHB therapists and assessors/screeners involved in delivery, assessments, or coordination of the intervention to ask them about their perspective on the same issues. Topics of interest for sub-group analyses include the effects of transitioning from in-person to by-phone format during the COVID pandemic, distress related to COVID-19, and the effects of prior miscarriage on current pregnancy and intervention experience.

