The intervention (i.e. the HMHB sessions) will be provided by non-specialist providers, who will receive simplified training followed by regular supervision.(37) These trainers will have a university degree in the social sciences, at least one year of relevant work experience and knowledge of the local language, but no prior experience in mental healthcare delivery. During year one of the funded grant, they have received a six-day training. Further training will include practice in the field and regular group supervision. The data collection team ('assessors') and non-specialist providers ('trainers') will be continually monitored. During the training period, data collectors will be assessed for interrater reliability (IRR).

Enhanced Usual Care (EUC) Control Group: Women allocated to the control condition will receive EUC. The WHO recommends eight antenatal visits for a positive pregnancy experience(43) which we will be the target number of visits for EUC participants (depending on their gestational week). Visits will involve evaluating health status, discussing any concerns, and performing routine exams consistent with stage of pregnancy. For EUC medical staff at the hospital will receive additional mental health training. Transportation will also be provided or facilitated for participants to assist with attending appointments and up to two ultrasounds will be paid for by the study.

Healthy Controls (HC): For the purpose of this revised application we will add a 2nd control group of 100 women who have low or no anxiety or depressive symptoms (<8 on both the anxiety and depression sub-sections of the HADS). This will allow us to compare biological processes in a group of anxious women with the intervention, a group of anxious women without the intervention and compare them to these healthy controls (non-anxious or depressed, without the intervention).

All three Groups: All medical staff will be trained on the WHO Mental Health Gap Action Programme (mhGAP) curriculum on management and intervention for common mental disorders. Transportation will be reimbursed or provided for women in all three study arms and participants will be offered 400 rupees (\$4) or a mobile phone "top up" voucher of 400 rupees for participation. Participants will also be reimbursed the cost of ultrasounds indicated by their medical team at Holy Family Hospital.

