#### Control arm:

Women randomized to the control group will receive usual care. The WHO recommends eight antenatal visits to optimize a positive pregnancy experience (103) which we will be the target number of visits for study participants in the control group (depending on their gestational week). These visits will involve evaluating health status, discussing any concerns, and performing routine exams consistent with stage of pregnancy. Usual care will be slightly enhanced by medical staff at the hospital receiving additional training in mental health treatment to counsel participants. Please refer to Table 3 for details about the content and schedule of usual care.

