**Table 2: Description of Usual Care\***

Visit	Content	Timing of visits as per WHO recommendation	Recipients
Visit 1:	Assessment for anemia; dietary counselling about healthy eating and keeping physically active during pregnancy; folic acid supplements; counseling for common physiological symptoms; emphasizing eight antenatal care visits	Following recruitment	All participants recruited into the study (intervention and control arm)
Visit 2:	Assessment for anemia; dietary counselling about healthy eating and keeping physically active during pregnancy; Iron and folic acid supplements; vaccination; counseling for common physiological symptoms; emphasizing eight antenatal care visits	Second trimester	All participants recruited into the study (intervention and control arm)

Visit 3:	Assessment for anemia; dietary counselling about healthy eating and keeping physically active during pregnancy; Iron and folic acid supplements; vaccination; counseling for common physiological symptoms; emphasizing eight antenatal care visits	Second trimester	All participants recruited into the study (intervention and control arm)
Visit 4:	Assessment for anemia; dietary counselling about healthy eating and keeping physically active during pregnancy; Iron and folic acid supplements; counseling for common physiological symptoms; emphasizing eight antenatal care visits	Third trimester	All participants recruited into the study (intervention and control arm)
Visit 5:	Assessment for anemia; dietary counselling about healthy eating and keeping physically active during pregnancy; Iron and folic acid supplements; counseling for common physiological symptoms; emphasizing eight antenatal care visits	Third trimester	All participants recruited into the study (intervention and control arm)
Visit 6	Assessment for anemia; dietary counselling about healthy eating and keeping physically active during pregnancy; Iron and folic acid supplements; counseling for common physiological symptoms; emphasizing eight antenatal care visits	Third trimester	All participants recruited into the study (intervention and control arm)
Visit 7	Assessment for anemia; dietary counselling about healthy eating and keeping physically active during pregnancy; Iron and folic acid supplements; vaccination; counseling for common physiological symptoms; emphasizing eight antenatal care visits	Third trimester	All participants recruited into the study (intervention and control arm)

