The proposed study is a single-blind, individual randomized clinical trial. The assessment team, trial statistician, and PIs will be masked to allocation status of study participants. To maintain masking during the trial, intervention and assessment teams will not have any interaction during the trial, as they will be placed at separate locations within the Obstetrics Department of HFH. Furthermore, participants will be instructed not to disclose which type of treatment they are receiving to the assessment team. Fidelity of masking will be measured by having assessors guess the trial arm of each participant at the end of follow-up assessment. We hypothesize that assessors will only be able to correctly guess the condition of participants at a chance rate of nearly 50% at follow-up assessments, indicating that masking is maintained.

2. Will participants receive standard care or have current therapy stopped?

Each woman randomized into the HMHB intervention arm will receive the HMHB intervention program plus usual care. Women allocated to the control condition will get usual care (slightly enhanced) alone. The WHO recommends eight antenatal visits for positive pregnancy experience (43) which we will be the target number of visits for study participants in the control group (depending on their gestational week). These visits will involve evaluating health status, discussing any concerns, and performing routine exams consistent with stage of pregnancy. Usual care will also be enhanced by medical staff at the hospital receiving additional training in mental health treatment to counsel participants. Transportation will also be provided or facilitated for participants to assist with attending appointments and the study will pay for any ultrasounds needed.

3. Will you use a placebo or non-treatment group, and is that justifiable?

The control arm will receive a slightly enhanced version of usual care, which we consider is justifiable.

4. Explain when you may remove a participant from the study.

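### Care by arm is described inconsistently; on the better-supported reading the comparator is enhanced usual care in both arms, so contact is not matched and the objective names the wrong comparator

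*Combined protocol and SAP*

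**What the plan says.** The primary objective in Section I evaluates the intervention "compared with usual care alone". Section III.A then describes a control arm whose contact is increased so that its frequency equals that of the intervention arm. It justifies the comparison group as slightly enhanced in number of visits, staff training, transport and scan payment.

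Section V, item 5, question 2 states: "Each woman randomized into the HMHB intervention arm will receive the HMHB intervention program plus usual care". For the other arm it states: "Women allocated to the control condition will get usual care (slightly enhanced) alone". It then sets the eight-visit target for the control group. The Enhanced Usual Care paragraph and the Control arm paragraph in Section V set the same target for controls. The Control arm paragraph adds that hospital staff will be "receiving additional training in mental health treatment to counsel participants".

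Table 2 (which the text cites as Table 3) lists the eight visits, and its recipients column reads, for every one, "All participants recruited into the study (intervention and control arm)". The paragraph on all three groups assigns mental-health training of all medical staff, transport and scan reimbursement to every group.

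On scans, the Enhanced Usual Care paragraph says "up to two ultrasounds will be paid for by the study". The paragraph on all three groups says "Participants will also be reimbursed the cost of ultrasounds indicated by their medical team at Holy Family Hospital". Question 2 has the study paying for whatever scans are needed, with no number.

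**The concern.** What each randomised arm receives defines the treatment contrast, and here it has to be pieced together from passages that disagree. Section III.A reads as a contact-matched comparison: controls are seen more often so that attention is equal. Table 2 reads as an add-on comparison: both arms have the same antenatal schedule and HMHB sessions come on top.

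These support different conclusions. In a contact-matched trial, a lower CMD prevalence can be credited to the content of the sessions. In an add-on trial, it is the effect of the whole package, including the extra time with a provider. Either is a legitimate question, but the report can answer only the one that was delivered. The objective raises a further problem: a result against enhanced usual care is not a result against usual care alone, and the cost-effectiveness comparison uses the same control arm.

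**Working it through.** **Step 1: the plan's own figure.** Section III.B gives the inputs: "We assume an outcome prevalence of CMDs (postnatal depression episode and anxiety) at 30" per cent, a 30% relative reduction (to 0.70 × 30% = 21%), 85% power, 420 per arm and 30% attrition. No alpha is stated for the main trial; two-sided 0.05 is assumed.

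n per arm = [z(0.975)·√(2·p̄·(1−p̄)) + z(0.85)·√(p1(1−p1) + p2(1−p2))]² / (p1−p2)², with p̄ = 0.255

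= [1.960·√0.37995 + 1.036·√0.3759]² / 0.09² = (1.208 + 0.635)² / 0.0081 ≈ 420.

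420 / 0.70 = 600 enrolled per arm. The plan's figures reproduce and do not depend on the disputed wording.

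**Step 2: the passages side by side.**

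| Element | Tied to controls | Given to everyone |
|---|---|---|
| Visits and contact | Section III.A (control contact raised); Enhanced Usual Care paragraph, Control arm paragraph and question 2 (eight-visit target) | Table 2, all eight visits; text after Table 2, routine care in both arms |
| Staff mental-health training | Section III.A (comparison group); Enhanced Usual Care and Control arm paragraphs | Paragraph on all three groups; Section V, question 6; Section VII (all obstetric medical staff) |
| Transport | Section III.A; Enhanced Usual Care paragraph | Paragraph on all three groups |
| Scan payment | Section III.A; Enhanced Usual Care paragraph (up to two) | Paragraph on all three groups (as indicated); Section IX (no arm limit) |

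The left column rests on where sentences sit and on the missing word enhanced for HMHB women. The right column assigns care expressly. Nothing in either column excludes HMHB women.

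**Step 3: does contact match?** HMHB consists of 6 core and 2 to 6 booster sessions, so 6 + 2 = 8 to 6 + 6 = 12 sessions, each of 45 to 60 minutes.

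- *Both arms on the Table 2 schedule.* Controls have a target of 8 visits. HMHB women have the same 8 plus 8 to 12 sessions, which is 8 × 45 = 360 minutes (6 hours) to 12 × 60 = 720 minutes (12 hours) of additional time.
- *Counting separate occasions instead.* Boosters are delivered at routine antenatal visits, so only core sessions can add trips. Table 2 places three visits before the third trimester. Assume the five weekly sessions finish before the third-trimester visits start. Then at most three can share a visit, leaving at least 5 − 3 = 2 extra occasions, with session 6 sharing a later visit. If no core session shares a visit, there are 6 extra. That gives 10 to 14 occasions against 8.
- *Eight visits for controls only.* This gives 8 visits against 8 to 12 sessions, equal only at the lower end. It also needs HMHB women to have no antenatal visits of their own, which "Each woman randomized into the HMHB intervention arm will receive the HMHB intervention program plus usual care" and the booster arrangement contradict.

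Section III.A's matching statement and Table 2 therefore cannot both stand.

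**Step 4: the objective.** Controls are enhanced in every detailed description of their care. Usual care alone, as named in Section I, matches none of them.

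**The case against.** The strongest reply is that this is loose drafting around a clear design. The paragraph on all three groups is explicit, all obstetric staff are trained, Section IX pays for scans without regard to arm, and question 2 itself says that usual care will be enhanced, without limiting that sentence to controls. Section III.A openly describes and justifies a slightly enhanced comparator, so usual care alone in the objective is shorthand. Much of this stands, and it is why the add-on reading is preferred here. It does not rescue the contact-matching statement, which fails on exactly that reading, or the objective, which a reader will take literally.

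A reader might go further and infer that only controls receive mental-health counselling, so that the CMD difference is narrowed and power lost. The documents do not support this. The training covers the whole department, no means of restricting it by arm is described, and no passage denies it to HMHB women. Nor do the documents give an effect size for counselling, so any power figure built on it would be invented.

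Two other inferences also fail. A limit of two paid scans would not clearly distort fetal data, since the note to Table 2 expects typically one scan in each of the second and third trimesters. And nothing shows that the assumed 30% prevalence ignored the enhancements; Section III.B says only that it is conservative. The absence of counselling from Table 2 is likewise no contradiction, because staff trained to counsel need not do so at every visit.

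**Conclusion.** The inconsistency is real and concerns what each arm receives. It is clearest for visits and contact, where the passages conflict directly, and for scan payment. For training and transport the express text points to everyone.

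Taken together, the documents favour HMHB plus enhanced usual care versus enhanced usual care. This is a reading of the text, not a confirmed fact about delivery. On it, HMHB women are offered 8 to 12 additional sessions (6 to 12 hours), so contact is not matched. The count of 10 to 14 occasions against 8 rests on the timing assumption above and on all eight visits being attended, although the target itself varies with gestational week. That the objective's comparator differs from the one described holds on any reading.

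The sample size is not in error, and no loss of power is claimed. What is affected is the conclusion the trial may state.

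**What to change.** - Reconcile Section I, Section III.A, the Enhanced Usual Care, all-three-groups and Control arm paragraphs, Table 2 and question 2, so that one statement says which enhancements and which visit target each arm receives and how scans are paid. Which rule applies is for the investigators to settle.
- Restate the primary objective and the planned conclusion so that they name the reconciled comparator.
- If both arms have the same visit schedule, correct or drop the statement that contact frequency matches, and describe any effect as that of the HMHB package including its added contact.
- Report antenatal visits attended and mental-health counselling by hospital staff, by arm. The service-use instrument in Table 4 (third trimester and six weeks postpartum) may supply part of this. The documents do not say whether it separates out such counselling, so an item may need adding.

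The cost is protocol wording and a small reporting task. The downside is a stated comparator that sounds less favourable than usual care alone.
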